7.2 Analysis of secondary efficacy endpoints

Definitions and data conventions

Number of re-hospitalizations and death

The number of re-hospitalizations and deaths will be calculated per-subject as the sum of the number of hospitalizations as recorded in the ‘COPD Exacerbation Form’ and the deaths (all cause).

Number of moderate/severe COPD exacerbations

The number of moderate/severe COPD exacerbations will be calculated per-subject as the sum of the number of COPD exacerbations recorded as “Moderate” or “Severe” in the ‘COPD Exacerbation Form’.

Number of pneumonia events

The number of pneumonia events will be calculated per-subject as the sum of adverse events classified with the following System Organ Classes/Preferred Terms:

System Organ Class	Preferred Term
Respiratory, thoracic and mediastinal disorders	
 • Pneumonia NOS • Acute pneumonia • Lung infection • Multilobar pneumonia • Bronchopneumonia • Pneumonia lobar • Pneumonia, organism unspecified • Bronchopneumonia NOS • Acute bronchopneumonia • Community acquired pneumonia • Lobar pneumonia NOS • Ventilator associated pneumonia • Healthcare associated pneumonia • Pneumonia recurrent • Bronchopulmonary infection

Forms			
Title	Statistical Analysis Plan Template		
Code	Version	Effective Date	Page
FRM_ST03_032	02	02 Oct 2017	20 of 26

	
 Pulmonary suppuration Lung infection NOS Pleuropneumonia Bronchopneumonia, organism unspecified Bilateral bronchopneumonia Infectious pneumonitis Nosocomial pneumonia Bronchial pneumonia Bilateral pneumonia Hospital acquired pneumonia Right middle lobe pneumonia Lobar pneumonia
--	---

Number of acute cardiac events

The number of acute cardiac events will be calculated per-subject as the sum of adverse events classified with the following System Organ Classes/Preferred Terms:

System Organ Class	Preferred Term
Cardiac disorders	
 Heart failures -Coronary artery disorders Cardiac arrhythmias Embolic stroke Haemorrhagic stroke Thrombotic stroke

Time on study

Time on study (years) will be calculated using the following formula:

Time on study (years) = (Date of patient completion or withdrawal - Date of randomization +1)/365.25.

Log-time on study (years)

The log-time on study in years will be calculated using the following formula:

$$\text{Log-time on study} = \ln(\text{time on study})$$

Statistical analysis

Analysis will be performed on the ITT population.

Number of re-hospitalizations and deaths

The number of re-hospitalizations and deaths of all cause (1, 2, 3, 4, >4) will be summarised by using frequency distributions and percentages.

Comparison between treatments will be performed using a Poisson regression model. The model will include the number of events as dependent variable, treatment group and center as qualitative independent variables and age as quantitative independent variable. Log-time on study (in years)

Forms			
Title	Statistical Analysis Plan Template		
Code	Version	Effective Date	Page
FRM_ST03_032	02	02 Oct 2017	21 of 26

will be used as an offset. The overdispersion parameter based on the deviance will be considered in order to account for between-patient variability in the event rate and standard errors will be estimated allowing for extra-Poisson variation.

The number of patients and the number of patients considered in the model will be provided by treatment. P-values of the independent variables based on Wald chi-square test will also be presented.

The adjusted mean rates per patient per year in each treatment group and their 95% CIs will be presented, and the adjusted rate ratio between treatments will be provided with the associated 95% Wald CI and p-value.

The following SAS® code will be used to estimate the Poisson regression model:

```
proc genmod data = dataset;
class TMT CENTER;
model VAR = TMT CENTER AGE / offset=log_time dist=poisson link=log dscale wald type3;
lsmeans TMT / exp cl;
lsestimate 'LABD vs LABD + ICS' TMT 1 -1 / exp cl;
run;quit;
```

where VAR represents the number of re-hospitalizations and deaths, TMT the treatment group, CENTER the center, AGE the age and log_time the logarithm of the time on study in years.

The variable tmt will be ordered in SAS in the following order:

- 1 = LABD;
- 2 = LABD + ICS.

Number of moderate/severe COPD exacerbations

The same analyses described for the number of re-hospitalizations and deaths will be performed for the number of moderate/severe COPD exacerbations (1, 2, 3, 4, >4).

Number of pneumonia events

The same analyses described for the number of re-hospitalizations and deaths will be performed for the number of pneumonia events (1, 2, 3, 4, >4).

Number of acute cardiac events

The same analyses described for the number of re-hospitalizations and deaths will be performed for the number of acute cardiac events (1, 2, 3, 4, >4).

Number of deaths

Patients who died will be presented with a breakdown of the causes of death (Cardiovascular death/Other) by treatment and overall.

QoL variation (change in CAT total score from baseline to end of treatment period)

CAT total score, the change from baseline will be summarised by treatment at each visit by means of descriptive statistics. 95% CIs for the mean change will also be calculated.

Forms			
Title	Statistical Analysis Plan Template		
Code	Version	Effective Date	Page
FRM_ST03_032	02	02 Oct 2017	22 of 26

A comparison between treatment groups will be performed with an ANCOVA model with the change from baseline of the CAT total score to the end of treatment period (i.e. Visit 6) as dependent variable, treatment group and centre as qualitative independent variables and age and baseline value of the variable as quantitative independent variables.

The number of patients and the number of patients considered in the model will be provided by treatment. P-values of the independent variables will also be presented.

The adjusted means for treatments and the relative 95% CIs will be presented. The difference between the adjusted means for LABD and LABD + ICS will be calculated with the relative 95% CI and p-value.

The following SAS® code will be used to estimate the ANCOVA model:

```
proc mixed data = dataset;
class TMT CENTER;
model CHG = TMT CENTER AGE BASELINE;
lsmeans TMT / cl;
lsestimate 'LABD vs LABD + ICS' TMT 1 -1 / cl;
run;
```

where CHG represents the change from baseline of the CAT total score at Visit 6, TMT the treatment group, CENTER the center, AGE the age and BASELINE the baseline value of the variable.

The variable TMT will be ordered in SAS in the following order:

- 1 = LABD;
- 2 = LABD + ICS.

Change in mMRC dyspnea score from baseline to end of treatment period

The same analyses described for the change in CAT total score will be performed for the change in mMRC dyspnea score.

Change in FEV1 from baseline to the end of treatment period

The same analyses described for the change in CAT total score will be performed for the change in FEV1.

Change in FVC from baseline to the end of treatment period

The same analyses described for the change in CAT total score will be performed for the change in FVC.

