8.1.3. Assessment of number of pneumonia events

Pneumonia events will be recorded based on the clinical diagnosis and will be confirmed by chest x-ray where possible.

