2.2 Secondary objectives

Secondary objectives are the following:

- to compare the number of moderate/severe exacerbations of COPD in the two patient groups;
- to compare the number of re-hospitalizations and deaths (all cause) in the two patient groups;
- to compare Quality of Life (QoL) scores measured using the COPD Assessment Test (CAT) and modified Medical Research Council (mMRC) dyspnoea scale between the two patient groups;
- to verify if one year of treatment with combination therapy including ICS increases the risk of pneumonia;
- to compare the number of acute cardiac events in this frail, elderly COPD population;
- to compare the incidence of deaths due to cardiovascular events;
- to compare changes in lung function.

3. Study Design

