8.1 Adverse events

Definitions and data conventions

Pre-treatment adverse events

An AE will be classified as pre-treatment AE if it starts before the date of randomization (AE onset date < date of randomization).

Treatment-emergent adverse event (TEAE)

An AE will be classified as a TEAE if it starts on or after the date of randomization (AE onset date \geq date of randomization).

In case of missing or incomplete dates not allowing a direct allocation to any of the two categories of AEs, a worst-case allocation will be done according to the available parts of the onset and the end dates. The AE will be allocated to the first category allowed by the available data, according to the following order:

- TEAE
- Pre-treatment.

Serious adverse event (SAE)

A SAE is an AE judged as serious.

Adverse drug reaction (ADR)

An ADR is an AE with relationship to study treatment equal to “Yes”.

Severe adverse event (SAE)

A SAE is an AE judged as severe intensity.

Adverse event leading to study withdrawal

An AE leading to study withdrawal is an AE with action taken equal to “Drug withdrawn” or “Drug interrupted”.

Count of adverse events

Two AEs with the same Preferred Term (PT) and classified in the same category (pre-treatment AE or TEAE) will be considered as two different events when calculating the “number of events” in the tables.

Statistical analysis

Pre-treatment AEs and TEAEs will be presented separately. Pre-treatment AEs will be presented in the listings only.

The number of treatment-emergent AEs, SAEs, ADRs, severe AEs and AEs leading to discontinuation, and the number and the percentage of patients experiencing treatment-emergent AEs, SAEs, ADRs, severe AEs and AEs leading to discontinuation will be summarised by treatment group. Differences between groups will be evaluated using Chi-square test or Fisher’s exact test (if more than 20% of the cells in a contingency table have expected counts less than 5).

Title	Statistical Analysis Plan Template		
-------	------------------------------------	--	--

Code	Version	Effective Date	Page
FRM_ST03_032	02	02 Oct 2017	24 of 26

AEs will be coded using the MedDRA dictionary (version 21.0). The SOCs and PTs will be used for tabulation. The number of treatment-emergent AEs and the number and the percentage of patients with at least one treatment-emergent AE will also be presented by SOC and PT by treatment group.

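### The SAP's pneumonia count uses one respiratory organ class and 27 terms that omit plain Pneumonia, so some clinically diagnosed pneumonias can drop out of the ICS-pneumonia comparison

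*SAP*

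**What the plan says.** One of the secondary objectives in SAP 2.2 is "to verify if one year of treatment with combination therapy including ICS increases the risk of pneumonia". For recording, Protocol 8.1.3 states: "Pneumonia events will be recorded based on the clinical diagnosis and will be confirmed by chest x-ray where possible". It gives no term list.

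SAP 7.2 supplies the counting rule: "The number of pneumonia events will be calculated per-subject as the sum of adverse events classified with the following System Organ Classes/Preferred Terms". The table that follows has a single organ class, "Respiratory, thoracic and mediastinal disorders", and 27 entries in a column headed as Preferred Terms. The two entries closest to an unspecified pneumonia are "Pneumonia NOS" and "Pneumonia, organism unspecified". The resulting count goes into the overdispersed Poisson model with treatment, centre, age and a log-time offset.

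SAP 8.1 says that adverse events are coded in MedDRA 21.0 and adds: "The SOCs and PTs will be used for tabulation". SAP 4.8 declares two changes from the protocol's analyses: paired t-test p-values are dropped, and vital signs and physical examination are only listed. The pneumonia rule is not among them.

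**The concern.** The column heading in SAP 7.2 names a coded field that SAP 8.1 says will exist in the data. A programmer would naturally match on that field and on the organ class. An adverse event whose coded term is plain *Pneumonia* would then add nothing to the pneumonia count, although it is a pneumonia event under the protocol.

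The list itself suggests that it was not built at Preferred Term level. It has *Lobar pneumonia*, *Lobar pneumonia NOS* and *Pneumonia lobar*, and it has *Lung infection* beside *Lung infection NOS*. These read as alternative wordings of the same diagnosis.

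The Introduction of the protocol gives pneumonia as the more important of two reasons for restricting ICS. The Poisson model is the only planned analysis that yields a pneumonia rate ratio with a confidence interval. For a question about harm, a count that loses events tends towards an inconclusive result, and readers may take that as reassurance.

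**Working it through.** **1. Check of the list.** The 27 entries are all distinct. A case-insensitive exact match for *Pneumonia* finds none. No entry names aspiration, a virus, a bacterium or another organism. Four entries do not contain the stem of the word pneumonia: *Lung infection*, *Lung infection NOS*, *Bronchopulmonary infection* and *Pulmonary suppuration*. One organ class is shown, and no infections class appears.

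**2. The two rules side by side.**

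| Event | Protocol 8.1.3 | SAP 7.2 as written |
|---|---|---|
| Clinical pneumonia, coded plain *Pneumonia* | event | not counted |
| Clinical pneumonia, coded with an organism-named, viral or aspiration term | event | not counted |
| Clinical pneumonia, coded with a listed term but under another organ class | event | not counted if the class is a condition |
| *Lung infection* under the respiratory class | event only if clinically diagnosed as pneumonia | counted |

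**3. Plan figures.** The documents give no pneumonia rate, ICS effect, power or code frequency, so there is no plan figure for this endpoint to reproduce and no corrected count to derive. The only design figure is for the primary endpoint, and it does reproduce. HR = ln(0.91)/ln(0.85) = 0.580. Freedman events = (1.960 + 0.842)² × (1.580/0.420)² = 111.3. The number per group is 111.3/(0.09 + 0.15) = 463.7, so 464, and 464/0.9 gives 516. Only the 464 is used below.

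**4. Effect of losing events.** Let c be the share of events retained, equal in both arms.

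- Rate ratio: (c·r₁)/(c·r₀) = r₁/r₀, unchanged in expectation.
- Absolute rates: multiplied by c.
- SE of the log rate ratio ≈ sqrt(φ(1/E₁ + 1/E₀)). With the dispersion φ unchanged, it is multiplied by 1/sqrt(c): 1.15 at c = 0.75, 1.41 at c = 0.50, 2.00 at c = 0.25 and 3.16 at c = 0.10.

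**5. Illustration, by assumption only.** Take 464 per arm, a LABD pneumonia rate of 5% and a true ratio of 2.0, with a two-proportion approximation for power. Expected events with none lost are 464 × 0.05 × (1 + 2) = 69.6.

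| Share lost | Events counted | Power |
|---|---|---|
| 0% | 69.6 | 82.5% |
| 25% | 52.2 | 69.9% |
| 50% | 34.8 | 51.8% |
| 75% | 17.4 | 28.9% |
| 90% | 7.0 | 14.1% |

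Over rates of 3% to 8% and ratios of 1.5 to 2.0, power runs from 22–96% with none lost, to 13–73% with half lost, to 6–20% with 90% lost.

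The interval for the same 5% and 2.0 case, with φ = 1:

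- None lost: E = 23.2 and 46.4. SE = sqrt(1/23.2 + 1/46.4) = 0.254. The 95% CI around 2.0 is 2.0 ÷ and × exp(1.96 × 0.254), or about 1.21 to 3.29.
- Half lost: E = 11.6 and 23.2. SE = 0.360. The interval is about 0.99 to 4.05, which no longer excludes 1.

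**The case against.** The strongest reply is that the list plainly tries to catch unspecified pneumonia, through *Pneumonia NOS*, *Pneumonia, organism unspecified* and *Acute pneumonia*. If the entries are really reported-term wordings, the fault is a mislabelled coding level, and only an exact match on the Preferred Term field loses the plain diagnosis. The organ class may be just a table heading, since the rule joins class and term with a slash. The neighbouring cardiac table uses the same headings for broad groups. Protocol 8.1.3 says how sites record pneumonia and not how to count it, so a term list can be seen as technical elaboration. The *Lung infection* entries push the count upwards, so the net direction is not proven. All treatment-emergent events are tabulated by class and term under SAP 8.1, so nothing vanishes from the report.

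Much of this stands. A reader might infer that plain *Pneumonia* is the most common code, that most listed entries can never match, or that the count would approach zero because these terms sit under an infections class. Each of these needs the dictionary or the coded data, and the documents contain neither. A reader might also infer that the rate ratio is biased, but equal loss in both arms does not bias it. Nor do the documents rank this as a key safety endpoint: it is one of nine unranked secondary efficacy endpoints.

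The reply does not remove the gap. The SAP labels the column as Preferred Terms and names that field for tabulation. If the intent was looser, the text does not say so. The specific pneumonia terms are absent under either reading. The SAP 8.1 table gives counts and percentages by individual term, with no pneumonia total, rate ratio or exposure offset.

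**Conclusion.** The point holds as a defect in a stated counting rule. Read literally, SAP 7.2 excludes clinically diagnosed pneumonias coded with an omitted term or filed under another organ class. It does so in the one analysis that answers the ICS-pneumonia objective, and SAP 4.8 does not record the narrowing.

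The size of the under-count cannot be obtained from the documents. It depends on the share of events coded with omitted terms and on whether the organ class is applied as a filter. Given equal loss in both arms, the cost is in absolute rates and precision: about a 1.4-fold larger standard error if half are lost, and 2-fold if three quarters are lost. The power and interval figures rest on assumed rates and ratios and show only the order of the effect.

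This should be fixed before analysis. Confidence is medium, because the omissions can be read directly from the list but their practical weight depends on the MedDRA 21.0 hierarchy and the coded data.

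**What to change.** In SAP 7.2:

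- Remove the organ-class condition, so that an event counts by its term whatever class it is filed under.
- Rebuild the list from the Preferred Term level of MedDRA 21.0. Include plain *Pneumonia* and the organism-named (bacterial and other), aspiration and viral pneumonia terms. State that matching is done at that level.
- Have the list agreed before analysis by reviewers who see the coded terms without treatment group. The trial is open label, and SAP 4.9 places the Data Review Meeting after database lock, so a repair made then with allocation visible would be open to challenge.
- Record the definition, and its relation to Protocol 8.1.3, in SAP 4.8.

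Optionally, add a sensitivity count without the non-specific entries (*Lung infection*, *Lung infection NOS*, *Bronchopulmonary infection*, *Pulmonary suppuration*). Whether they belong in the main count is a choice between a broad and a narrow definition, and the correction does not depend on it.

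The cost is revised SAP wording and a short coding review. No new data are needed, and the Poisson model stays as planned.

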8.1.4. Acute cardiac events

Acute cardiac events will be recorded based on the clinical evaluation.

Acute CV events are defined as an inpatient or emergency department visit with a primary diagnosis of any of the following conditions (International Classification of Diseases, 9th Revision, Clinical Modification (ICD-9-CM) codes are also shown). Coronary heart disease (ICD-9-CM codes 410-414), cardiac arrhythmia (ICD-9-CM code 427), heart failure (ICD-9-CM code 428), or ischemic stroke (ICD-9-CM codes 433-434) (Wang et al 2018).

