3.3 Sample size justification

The sample size calculation is based on the superiority criteria of the LABD+ICS group versus LABD alone group in terms of re-hospitalization and/or death. With 464 patients in each group, the percentage of patients experiencing the composite event (re-hospitalization and/or death) is expected to be 9% in the LABD+ICS group and 15% in the LABD alone group. A log-rank test (two-sided 5% significance level) will have 80% power to detect a difference between treatment groups in terms of time to first re-hospitalization and/or death (primary efficacy endpoint). Adjusting for an expected 10% dropout rate, a total of 516 patients per group will need to be randomized.

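### The SAP's term list for acute cardiac events mixes class labels with stroke terms under one cardiac SOC, so the count depends on how it is read and departs from protocol 8.1.4 without being declared

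*SAP*

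**What the plan says.** Protocol 8.1.4 defines the event by care setting and diagnosis: "Acute CV events are defined as an inpatient or emergency department visit with a primary diagnosis of any of the following conditions". The conditions are "Coronary heart disease (ICD-9-CM codes 410-414), cardiac arrhythmia (ICD-9-CM code 427), heart failure (ICD-9-CM code 428), or ischemic stroke (ICD-9-CM codes 433-434").

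SAP 7.2 derives the count from coded adverse events instead: "The number of acute cardiac events will be calculated per-subject as the sum of adverse events classified with the following System Organ Classes/Preferred Terms". The only SOC shown is Cardiac disorders. The Preferred Term column reads: "Heart failures -Coronary artery disorders Cardiac arrhythmias Embolic stroke Haemorrhagic stroke Thrombotic stroke".

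On coding, SAP 8.1 says "AEs will be coded using the MedDRA dictionary (version 21.0") and "The SOCs and PTs will be used for tabulation". It names no intermediate dictionary level.

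The count is then tested between arms: "The same analyses described for the number of re-hospitalizations and deaths will be performed for the number of acute cardiac events", that is, by Poisson regression with an overdispersion parameter. SAP 4.8 lists two changes from the protocol, one on paired t-tests and one on vital signs and physical examination. The definition of acute cardiac events is not among them.

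**The concern.** A derivation rule should give the same count whoever programs it. This one leaves two things open: whether the three plural labels are terms to be matched or groups to be expanded, and whether the SOC column is a filter or only a caption. It also differs from the protocol's list of conditions without saying so.

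Comparing acute cardiac events is a named secondary objective, and protocol 5.1 requires every patient to have heart failure, ischaemic heart disease or atrial fibrillation. The trial is open label, and SAP 4.9 holds the Data Review Meeting after database lock. If the ambiguity is first noticed at programming or at that meeting, the list will be settled when events and treatment can both be seen.

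**Working it through.** **No figure to reproduce.** The documents give no rate, count or power for acute cardiac events. The expected percentages in the sample size section concern the primary composite, which "is expected to be 9% in the LABD+ICS group and 15% in the LABD alone group". The check is therefore a comparison of texts.

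**Step 1: set the two definitions side by side.**

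| Protocol 8.1.4 | SAP 7.2 entry | Exact PT match | Labels read as groups |
|---|---|---|---|
| Coronary heart disease (410-414) | Coronary artery disorders | An AE coded to myocardial infarction does not match | All AEs in the group count |
| Cardiac arrhythmia (427) | Cardiac arrhythmias | An AE coded to atrial fibrillation does not match | All AEs in the group count |
| Heart failure (428) | Heart failures | An AE coded to a specific form of heart failure does not match | All AEs in the group count |
| Ischaemic stroke (433-434) | Embolic stroke, thrombotic stroke | An AE coded simply as ischaemic stroke does not match | Same |
| Not included | Haemorrhagic stroke | Added | Added |
| Inpatient or emergency visit with primary diagnosis | No condition | Not applied | Not applied |

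The stroke rows hold if the SOC column does not exclude the stroke terms (step 3).

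The exact-match column assumes that MedDRA 21.0 carries specific diagnoses as PTs in their own right. The documents do not show the dictionary, but the pneumonia table in the same section, under the same column heading, lists 27 specific terms.

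**Step 2: the class labels.** The documents support both readings. The column heading and SAP 8.1 point to PT level. The protocol's code range for coronary disease, and the way the three labels parallel its three cardiac conditions, point to groups. Nothing in the SAP decides between them.

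**Step 3: the SOC column.** Strokes listed under a cardiac SOC look out of place on the face of the table. If MedDRA 21.0 files them elsewhere (an assumption), using the SOC as a filter removes all three, and using it as a caption keeps them. With step 2, this gives 2 × 2 = 4 possible derivations from the same data.

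**Step 4: direction of error.** Exact matching can under-count. Group matching can over-count against the protocol, because no visit or primary-diagnosis condition is applied and haemorrhagic stroke is added. The sign of the error is not fixed.

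**Step 5: what lost events would cost, by illustration only.** Assume 2 × 464 = 928 patients with one year each, a true rate r of 0.05 to 0.20 events per patient-year, equal arms and no overdispersion. The events per arm are e = 464 × r × capture share, and the 95% CI of the rate ratio is the estimate multiplied and divided by exp(1.96 × √(2/e)).

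- Full capture: e = 23.2 to 92.8, about 46 to 186 events in total, factor 1.78 to 1.33.
- 10% capture: e = 2.32 to 9.28, about 5 to 19 events in total, factor 6.2 to 2.5.
- No capture: the rate ratio cannot be estimated.

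The rates and capture shares are assumed. None can be taken from the documents.

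**The case against.** The strongest reply is that the group reading is the natural one. The three labels mirror the protocol's heart failure, coronary disease and arrhythmia, SAP 7.2 does not ask for an exact match or say that the SOC is a filter, and a sensible programmer would expand the labels. On that reading there are events to count and the model can be fitted. Embolic and thrombotic stroke also cover part of the ischaemic concept. SAP 8.1 still tabulates all treatment-emergent AEs by SOC and PT, and SAP 7.2 breaks deaths down into cardiovascular and other, so nothing vanishes from the report. The table was also read from a PDF: there is a stray hyphen before one entry, and a row or SOC cell for the strokes may have been lost.

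Much of this stands. A reader might infer that the rule returns almost no events, that the Poisson model cannot be fitted, or that every stroke is lost. The documents do not support that. It needs the MedDRA 21.0 hierarchy, which they do not contain, together with the least favourable reading of a table that may be damaged.

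The reply does not remove the point. The SAP never states the group reading, and that reading still adds haemorrhagic stroke, lacks a general ischaemic stroke entry and omits the protocol's visit condition. A lost SOC cell would weaken the argument about where the strokes sit, but it would not make the class labels single diagnoses or bring the stroke entries into line with the protocol.

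**Conclusion.** The point holds as one of reproducibility and undeclared departure. From the documents alone, the list mixes levels in a column headed as PTs, the SAP does not say how to read it, and on either reading of the labels its stroke entries and its missing visit condition differ from protocol 8.1.4 without mention in SAP 4.8.

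Its size is unknown. Under-capture on the exact-match reading assumes that specific diagnoses are PTs distinct from the three labels. Loss of the strokes assumes that their terms sit outside Cardiac disorders and that the SOC acts as a filter. Both need a look at MedDRA 21.0. On the group reading the error may run the other way.

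The effect is confined to one of nine secondary endpoints; the primary analysis is untouched. The list should be corrected, because the repair is cheap and is cleaner when made before the results are seen.

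**What to change.** In SAP 7.2, replace the table with an explicit list of MedDRA 21.0 PTs:

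1. All PTs under the heart failure, coronary artery disorder and cardiac arrhythmia groups, with the dictionary level of each group stated.
2. The ischaemic stroke PTs.
3. Matching on PT only, without the Cardiac disorders SOC condition.
4. Haemorrhagic stroke either removed, to agree with protocol 8.1.4, or kept and declared in SAP 4.8 as a departure.
5. A statement of how the protocol's inpatient or emergency visit and primary-diagnosis condition is applied to the AE records. If it cannot be applied, declare that in SAP 4.8 as well.

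Freeze the list before database lock, without reference to treatment arm. If lock has already passed, record it as a dated change made without reference to arm.

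The term list costs one dictionary extraction and a revision of SAP wording, with no new data. Whether item 5 can be met from existing data depends on what the eCRF records for each event, which the documents do not show.
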